9.1.1 Dose Modifications for Safety

9.1.1.1 Stopping Criteria

Individual Subject Stopping Criteria

For individual subjects, temporary dosing suspension, permanent discontinuation of dosing, or, in exceptional circumstances, dose reduction will be considered and DMC will be informed (at a minimum) if any of the following occur:

- Any TEAE at least Grade 3 assessed by the Investigator and/or Sponsor Medical Monitor
- Any two TEAEs Grade 2 experienced by the same subject within 1 week including two symptomatic hypotension events within 1 week (non-urgent medical intervention indicated) or any Grade 3 hypotensive event (urgent medical intervention or hospitalization indicated) assessed by the Investigator and/or Sponsor's Medical Monitor
- Prolongation of QTc-F interval to more than 500 msec, ventricular tachycardia greater than five beats
- Any clinically significant worsening of existing disproportionate growth, as determined by physical measurement ratios and/or Investigator assessment based on imaging, measurement or clinical observation findings
 - Upper arm to forearm length ratio
 - Upper leg to lower leg length ratio
 - Upper to lower body segment ratio
- Clinically significant worsening of bone morphology as evidenced by development of tibial bowing, or worsening of existing tibial bowing as observed via clinical or radiographic assessment
- Clinically significant worsening of elbow joint range of motion based on clinical assessment and on goniometry measurements of flexion-extension
- Findings on clinical hip exam or hip imaging assessments that are determined to be clinically significant as decided by principal investigator and in consultation with sponsor medical monitor and orthopedic specialist (if needed)

If the subject meets any stopping criteria, after Investigator consultation with the BioMarin Medical Monitor and DMC (if warranted), the subject may be re-challenged at the same dose. If the subject meets stopping criteria on re-challenge or if re-challenge at same dose is not clinically indicated, other options that may be considered include:

BOMARIN [®]	BMN 111-202 Amendment 4	Page 49
----------------------	-------------------------	---------

- Re-challenge at lower dose with consideration given to upward titration to tolerated dose/cohort dose
- Permanent treatment discontinuation (with and option of ongoing assessment in the study)

Cohort Stopping Criteria

For an open cohort and all higher dose cohorts, temporary dosing suspension or dose reduction will be considered and DMC review will be conducted (at a minimum) if any of the following occur:

- Any two subjects within a cohort have TEAE at least Grade 3; any two subjects have two symptomatic hypotension events within 1 week each Grade 2 (non-urgent medical intervention indicated); or any two subjects have a Grade 3 hypotension event (urgent medical intervention or hospitalization indicated) assessed by the Investigator and/or Sponsor Medical Monitor
- Any one subject with any TEAEs Grade 4 or 5 assessed by the Investigator and/or Sponsor Medical Monitor
- Any two subjects within a cohort have prolongation of QTc-F interval to more than 500 msec, ventricular tachycardia greater than five beats
- Any two subjects within a cohort have clinically significant worsening of existing disproportionate growth, as determined by physical measurement ratios and/or Investigator assessment based on imaging, measurement or clinical observation findings
 - Upper arm to forearm length ratio
 - Upper leg to lower leg length ratio
 - Upper to lower body segment ratio
- Any two subjects within a cohort exhibit clinically significant worsening of bone morphology as evidenced by development of tibial bowing, or worsening of existing tibial bowing as observed via clinical or radiographic assessment
- Any two subjects exhibit clinically significant worsening of elbow joint range of motion based on clinical assessment and on goniometry measurements of flexion-extension
- Any two subjects exhibit findings on clinical hip exam or hip imaging assessments that are determined to be clinically significant as decided by principal investigator and, if needed, in consultation with sponsor medical monitor and orthopedic specialist (if needed)
- Any other reason DMC advises temporary discontinuation of cohort dosing until further review of safety data is conducted

Sites have 1 business day to report to BioMarin an event that meets individual or cohort stopping criteria. DMC can ask for additional available data while reviewing subject(s) who met individual stopping criteria, or subjects with any other new safety finding. In order to assess significance of the findings, DMC can request to review additional data for other subjects in the cohort, or any other subjects in the study. These additional data include, but are not limited to, physical exam, vital signs, anthropometric measures, ECG, ECHO, and lab results. The DMC will review available, relevant safety data within 5-7 days after BioMarin is apprised of an event. BioMarin will keep all sites informed of enrollment pauses, to ensure that no subjects in the cohort (and all higher cohorts) that are affected by stopping criteria are treated, and no new subjects are enrolled, until the assessment is complete. Based on its review, the DMC may make any of the following recommendations:

- Continue cohort and sequential dosing of cohorts as planned with additional safety monitoring and/or safety reviews as indicated
- Continue current cohort, but higher dose cohorts will receive lower doses than planned
- Decrease cohort dose and decrease doses of subsequent cohorts
- Extend temporary treatment discontinuation until additional data are available and/or further review/consultation occurs
- Permanently discontinue treatment for all cohorts
- Dose additional subjects of the cohort at the same dose

Cohort doses may be changed, based on DMC review of safety and efficacy data, to any dose between 0.5 µg/kg and 30 µg/kg. Any subject who discontinues from study drug will be encouraged to complete assessments for the duration of the study.

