For individual subjects, temporary dosing suspension, permanent discontinuation of dosing, or, in exceptional circumstances, dose reduction will be considered and DMC will be informed (at a minimum) if any of the following occur:

- Any treatment-emergent adverse event (TEAE) at least Grade 3 assessed by the Investigator and/or Sponsor Medical Monitor
- Any two TEAEs Grade 2 experienced by the same subject within 1 week, including two symptomatic hypotension events within 1 week (non-urgent medical intervention indicated) or any Grade 3 hypotensive event (urgent medical intervention or hospitalization indicated) assessed by the Investigator and/or Sponsor's Medical Monitor
- Prolongation of QTc-F interval to more than 500 millisecond (msec), ventricular tachycardia

greater than five beats

- Any clinically significant worsening of existing disproportionate growth, as determined by physical measurement ratios and/or Investigator assessments based on imaging, measurement or clinical observation findings
 - Upper arm to forearm length ratio
 - Upper leg to lower leg length ratio
 - Upper to lower body segment ratio
- Clinically significant worsening of bone morphology as evidenced by development of tibial bowing, or worsening of existing tibial bowing as observed via clinical or radiographic assessment
- Clinically significant worsening of elbow joint range of motion based on clinical assessment and on goniometry measurements of flexion-extension
- Findings on clinical hip exam or hip imaging assessments that are determined to be clinically significant as decided by principal investigator and in consultation with sponsor medical monitor and orthopedic specialist (if needed).

If the subject meets any stopping criteria, after Investigator consultation with the BioMarin Medical Monitor and DMC, the subject may be re-challenged at the same dose. If the subject meets stopping criteria on re-challenge or if re-challenge at same dose is not clinically indicated, other options that may be considered include:

- Re-challenge at lower dose with consideration given to upward titration to tolerated dose/cohort dose
- Permanent treatment discontinuation (with an option of ongoing assessment in the study)

Cohort Stopping Criteria

For any open cohort and all higher dose cohorts, temporary dosing suspension or dose reduction will be considered and DMC review will be conducted (at a minimum) if any of the following occur:

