Sites have 1 business day to report to BioMarin an event that meets individual or cohort stopping criteria. DMC can ask for additional available data while reviewing subject(s) who met individual stopping criteria, or subjects with any other new safety finding. In order to assess significance of the findings, DMC can request to review additional data for other subjects in the cohort, or any other subjects in the study. These additional data include, but are not limited to, physical exam, vital signs, anthropometric measures, ECG, ECHO, and lab results. The DMC will review available, relevant safety data within 5-7 days after BioMarin is apprised of an event. BioMarin will keep all sites informed of enrollment pauses, to ensure that no subjects in the cohort (and all higher cohorts) that are affected by stopping criteria are treated, and no new subjects are enrolled, until the assessment is complete. Based on its review, the DMC may make any of the following recommendations:

- Continue cohort and sequential dosing of cohorts as planned with additional safety monitoring and/or safety reviews as indicated
- Continue current cohort, but higher dose cohorts will receive lower doses than planned
- Decrease cohort dose and decrease doses of subsequent cohorts
- Extend temporary treatment discontinuation until additional data are available and/or further review/consultation occurs
- Permanently discontinue treatment for all cohorts
- Dose additional subjects of the cohort at the same dose

Cohort doses may be changed, based on DMC review of safety and efficacy data, to any dose between 0.5 µg/kg and 30 µg/kg. Any subject who discontinues from study drug will be encouraged to complete assessments as appropriate for the duration of the study (Section 9.3.3).

Optional, Open-label Extension Phase of the Study

In the open-label, optional extension phase, the long-term safety, tolerability, and effects of BMN 111 on growth will be evaluated in children with ACH who have completed an initial 6 months of treatment with BMN 111. At the Day 183/6-month visit, subjects who elect to continue participating in the optional open-label extension phase will be consented for the extension phase. These subjects will receive study drug on Day 184 of the initial phase, which also marks the beginning of the extension phase. Drug treatment will continue without interruption. Subjects who decline to

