In the 18-month optional, open-label extension phase, subjects within each cohort will either remain on the same stable dose that they have been receiving during the initial 6 months of treatment, or the dose for all subjects in the cohort (except cohort 4) may be increased based on the following rules:

(1) Initial dose was determined to exhibit suboptimal efficacy on the basis of growth measurements after at least 6 months of treatment based on the review of the data for all subjects in the cohort.

(2) Initial dose, and other doses higher than the initial dose, but lower than the dose to which the cohort is being increased were generally well tolerated for at least 6 month based on review of data for all subjects in the cohort.

(3) The dose to which the subjects in the cohort are being escalated has been previously shown to be well tolerated for at least 10 days of comprehensive outpatient safety monitoring as described in Section 9.1, based on DMC review of the data for all subjects in the cohort previously assigned to the considered dose.

During the optional, open-label extension phase, visits will take place at 2- to 3-month intervals. The site will call the caregiver/subject between the visits every two weeks for the first 6 months and every month for the remainder of the study.

DMC data review will occur approximately every 4 months during the optional, open-label extension phase.

Subjects who participate in the open-label extension phase of study 111-202 will have the option to enroll in the long-term extension study 111-205 at the Month 24/Study Completion Visit. Month 24 assessments will serve as Baseline/screening assessments for entry to study 111-205.

Criteria for Dose Adjustment Visits

The timing of dose adjustments and follow-up visits after adjustment is contingent upon the time at which the dose adjustment was recommended. One of two scenarios will apply:

- Scenario 1: Recommendation to adjust the dose is made when the next scheduled visit is ≤ 4 weeks away from the date that the dose change is communicated to sites. Dose adjustment will be done at the next scheduled visit.
- Scenario 2: Recommendation to adjust the dose is made when the next scheduled visit is > 4 weeks away from the date that the dose change is communicated to sites. An unscheduled dose adjustment visit will be done within 4 weeks.

[figure not shown]

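### Once Cohorts 1 and 2 move to 15 µg/kg, the interim dosing hold does not name children in other cohorts who are on the same dose as the triggering cohort

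*Protocol*

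**What the plan says.** Protocol section 9.1.1.1 gives the scope of a cohort-level safety action twice, in different words.

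- The lead-in to the cohort stopping criteria reads "For an open cohort and all higher dose cohorts, temporary dosing suspension or dose reduction will be considered". The synopsis has the same scope: "For any open cohort and all higher dose cohorts, temporary dosing suspension or dose reduction will be considered".
- The later sentence governs the period while an event is being assessed. It sets the sponsor this goal: "no subjects in the cohort (and all higher cohorts) that are affected by stopping criteria are treated, and no new subjects are enrolled". The synopsis repeats it: "no subjects in the cohort (and all higher cohorts) that are affected by stopping criteria are treated".

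On timing, section 9.1.1.1 states "The DMC will review available, relevant safety data within 5-7 days after BioMarin is apprised of an event".

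Protocol section 9.1 then allows cohort and dose to separate in the extension: "the dose for all subjects in the cohort (except cohort 4) may be increased based on the following rules". Under the third of those rules, the target dose must have been "previously shown to be well tolerated for at least 10 days of comprehensive outpatient safety monitoring". SAP section 2.2 records the outcome. Eligible children in Cohorts 1 and 2 were raised to 15 µg/kg, Cohort 3 stayed at 15 µg/kg and Cohort 4 at 30 µg/kg. SAP sections 3.2 and 14 accordingly summarise extension safety by dose level. That governs analysis, not dosing.

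**The concern.** While each cohort has its own dose, a hold on one cohort and those above it is a hold on the suspect dose and everything higher. After escalation, three cohorts share 15 µg/kg and that equivalence is lost. Followed as written, the rule can reach children on 30 µg/kg and pass over children on the very dose that raised the concern.

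The escalation rules do not prevent this. They ask for six months of tolerance at the starting dose and any intermediate doses, but only 10 days at the target dose. An event at 15 µg/kg in Cohort 3 can therefore arise after the other cohorts have joined that dose. Protocol section 7.1 describes the adverse skeletal changes seen in animals as depending on time as well as dose and exposure, so late triggers are plausible.

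**Working it through.** **Inputs.** Cohort sizes are 8, 8, 8–10 and 8–10 (Protocol 9.1). Dosing is daily, seven days a week (9.4.1). DMC review takes 5–7 days (9.1.1.1). The documents reviewed do not say how many children escalated, so it is treated as an unknown k, from 0 to 16.

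**Plan's own total.** 8 + 8 + 8 + 8 = 32, and 8 + 8 + 10 + 10 = 36. The stated figure of approximately 36 is the upper end.

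**Who is covered after escalation to 15 µg/kg.**

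| Trigger in | Hold sentence (cohort and higher cohorts) | On the same dose but not named |
|---|---|---|
| Cohort 1 (15 µg/kg) | Cohorts 1–4 | none |
| Cohort 2 (15 µg/kg) | Cohorts 2–4 | Cohort 1 |
| Cohort 3 (15 µg/kg) | Cohorts 3–4 | Cohorts 1 and 2 |
| Cohort 4 (30 µg/kg) | Cohort 4 | none |

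For a Cohort 3 trigger, the lead-in wording (higher dose cohorts) gives the same answer. Escalated Cohort 1 and 2 children are on an equal dose, not a higher one.

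**Share not covered after a Cohort 3 trigger.** Share = k / (k + n3), where n3 is the size of Cohort 3, 8 to 10.

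- k = 16 (all): 16/26 = 61.5% to 16/24 = 66.7%.
- k = 8 (half): 8/18 = 44.4% to 8/16 = 50.0%.
- k = 4 (a quarter): 4/14 = 28.6% to 4/12 = 33.3%.

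**Share not covered after a Cohort 2 trigger, hold sentence, all escalated.** Cohort 1 is missed: 8/26 = 30.8% to 8/24 = 33.3%.

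**Children covered after a Cohort 3 trigger.**

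- As written: Cohorts 3 and 4, 8 + 8 = 16 to 10 + 10 = 20.
- By current dose of 15 µg/kg or more, all escalated: 32 to 36.
- Difference: 16.

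**Exposure during review.** Each child not covered has 5–7 scheduled doses. The arithmetic ceiling over all such children is 16 × 5 = 80 to 16 × 7 = 112 doses.

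**The case against.** The strongest reply is that the hold is less firm than it looks and that other protections exist. Much of this stands.

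- The lead-in puts suspension or dose reduction as something to consider, while the later sentence says affected children are not treated. An open cohort is not defined for the extension. If suspension is discretionary, equal-dose children differ less from the named cohorts. Even so, the scope to be considered leaves them out.
- Investigators may suspend drug at any time (Protocol 9.3.3). The sponsor and investigator must take urgent safety measures against immediate hazards (10.7). The DMC is told of single individual stopping events and can ask for data on any child. These powers narrow the consequence, but none is a pre-specified hold.
- For slowly developing findings such as bowing, disproportion or hip changes, five to seven more doses add little to months of exposure.

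Four stronger readings are tempting, and the documents do not support them.

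1. *The children outside the hold would certainly be dosed through the review, up to 112 doses in all.* That needs all 16 to enter an optional extension and escalate, and nobody to act early. SAP 2.2 says only that eligible children escalated.
2. *A Cohort 2 trigger misses 67–69% of children on 15 µg/kg.* That figure, (8 + 8)/24 to (8 + 10)/26, treats Cohort 3 as uncovered because its dose is equal. It rests on the lead-in wording, where suspension is only considered. The hold sentence covers Cohort 3, so the figure for the hold is 31–33%.
3. *The trigger counts should also be pooled by dose.* Four criteria (Grade 3 or higher events, QTc-F or ventricular tachycardia, disproportion, bowing) count two children in one cohort; others do not: "Any two subjects within a cohort have TEAE at least Grade 3; any two subjects have two symptomatic hypotension events within 1 week". Pooling would change a safety threshold. As illustration, assume independent events, a common per-child Grade 3 risk p (not in the documents) and all 16 escalated. P(at least 2 of n) = 1 − (1−p)^n − np(1−p)^(n−1). The chance that at least one of Cohorts 1–3 triggers separately, against the chance pooled over 24–26 children, is 3.1–3.6% against 8.3–9.5% at p = 2%, 16–19% against 34–38% at p = 5%, and 46–51% against 71–75% at p = 10%. That is a trade-off, not a correction.
4. *Sites would not be told of the dosing hold.* Section 9.1.1.1 already has the sponsor inform all sites so that affected children are not treated.

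**Conclusion.** The gap in scope is real. No section of the protocol or SAP redefines the hold by current dose, and after escalation neither wording names children in another cohort on an equal dose when Cohort 3 triggers. At most 16 of 24–26 children on 15 µg/kg (62–67%) are left out, falling to 29–33% if a quarter escalate. Under the hold sentence, a Cohort 2 trigger leaves out at most 8 of 24–26 (31–33%). These shares assume the planned cohort sizes, and the maxima assume that every Cohort 1 and 2 child escalates.

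The practical consequence is small: mainly a few extra daily doses per child before the DMC review, and fewer if the sponsor or an investigator steps in. A reader might infer that children at the suspect dose are left unprotected. The documents do not support that, because individual stopping criteria, discretionary suspension and DMC review all remain. This is a minor wording correction to a safety rule, for the sponsor to consider.

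**What to change.** In Protocol section 9.1.1.1 and the synopsis, keep the present scope and add one sentence:

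*The same applies to every subject whose current dose equals or exceeds the lowest dose at which a triggering event occurred, whatever the enrolment cohort, until the DMC gives its recommendation.*

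Because it extends whatever action applies to the named cohorts, the sentence works whether the hold is automatic or discretionary. Leave the trigger counts and the site-notification text as they are.

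The cost is a wording amendment, with no new visits or data. The downside is an occasional dosing interruption of about 5–7 days for up to 16 more children after a Cohort 3 trigger.

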9.1.2 Dose Modifications for Efficacy

Dose modifications for efficacy are discussed in Section 9.1 (subsection *Optional, Open-label Extension Phase of the Study*).

9.2 Discussion of Study Design, Including Choice of Control Group

The intent and design of this Phase 2 study is to assess BMN 111 as a therapeutic option for the treatment of children with ACH. Children 5-14 years old with ACH were chosen because subjects with ACH have an *FGFR-3* gain of function mutation and because preliminary efficacy evaluation, determined by change in annualized growth velocity, requires treatment of subjects prior to epiphyseal growth plate closure, which occurs in late adolescence. Growth velocity in children with ACH remains relatively stable from approximately 3 years

	BMN 111-202 Amendment 4	Page 51
---	-------------------------	---------

old to growth plate closure (Hoover-Fong, 2008, Am.J Clin Nutr.). Children younger than 5 years old will not be enrolled in order to establish a safety profile in an older population first, as well as to minimize the confounding effects of nonlinear growth rates and inaccuracies inherent in measurement of recumbent length in young children. As children with ACH do not experience the normal physiological growth acceleration associated with puberty (Hoover-Fong, 2008, Am.J Clin Nutr.) that could confound the data, the population is not limited to pre-pubescent children. A maximum of five children from one gender may be enrolled in each cohort if the total size of the cohort is eight or nine subjects; a maximum of six children from one gender can be enrolled in each cohort if the size of the cohort is 10 subjects.

9.3 Selection of Study Population

Subjects 5-14 years old (inclusive) who have documented ACH, as documented by clinical grounds and confirmed by genetic testing, were selected to participate in this study. Additional criteria for participation in the study are provided in Sections 9.3.1 and 9.3.2.

9.3.1 Inclusion Criteria

Individuals must meet the following inclusion criteria to be eligible to participate in this study:

1. Parent(s) or guardian(s) are willing and able to provide written, signed informed consent after the nature of the study has been explained and prior to performance of any research-related procedure. Also, subjects under the age of 18 are willing and able to provide written assent (if required by local regulations or the IRB/EC) after the nature of the study has been explained and prior to performance of any research-related procedure.
2. Are 5 to 14 years old, inclusive, at study entry
3. Have ACH, documented by clinical grounds and confirmed by genetic testing
4. Have at least a 6-month period of pretreatment growth assessment in Study 111-901 immediately before study entry, and have one documented standing height at least 6 months (+/- 10 days) prior to the screening visit for 111-202
5. Females ≥ 10 years old or who have begun menses must have a negative pregnancy test at the Screening Visit and be willing to have additional pregnancy tests during the study.
6. If sexually active, willing to use a highly effective method of contraception while participating in the study
7. Are ambulatory and able to stand without assistance
8. Are willing and able to perform all study procedures as physically possible

BOMARIN[®]	BMN 111-202 Amendment 4	Page 52
----------------------------	-------------------------	---------

9. Parents or caregivers are willing to administer daily injections to the subjects

Additional Inclusion Criteria Optional, Open-label Extension Phase:

1. Appropriate written informed consent (and assent, if applicable)

